7.5. Schedule

Only TAAD patients undergoing open heart surgery between 1 January 2010 and 31 December 2024 will be retrospectively retrieved and enrolled in the study. Deadline for submission of data is set up for 31 December 2021.

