8.2. Sample Size Calculation

The impact of total aortic arch repair compared to more limited aortic resection on the early and late outcomes will be one of the main topics of research from this registry. Therefore, in the light of the expected limited frequency of this surgical strategy, we performed a sample size analysis considering the extent of distal aortic resection. Despite the limitation of a pooled analysis which did not take in to account the cumulative incidences from competing risk analysis and the segment of repeat operation, Poon et al. (24) estimated a pooled hazard ratio on 0.73 (95%CI 0.56-1.18) of freedom from any late aortic reoperation for total arch replacement. Based on this hazard ratio, a sample size of 163 patients per study groups would be enough to reject the null hypothesis (alpha 0.05, power 0.80). Pan et al. (25) reported a freedom from distal reoperation after ascending aortic resection at 8 years of 95.3% which was not statistically different from that of hemiarch or total aortic arch repair (92.4%, p=0.22). For the sample size calculation of a non-inferiority trial, we assumed a freedom rate from distal aortic reoperation of 95% and we considered that a difference in the reoperation rate as large as 10% in favor of a total aortic arch repair still allow the less extensive repair to be non-inferior (delta=0.1, power 0.90, one-sided confidence 97.5%), the required sample size would be 100 patients per each group. We assume that about 5% of patients have undergone total arch repair in this collaborative registry and therefore a study population of 4000 patients would be enough to investigate the impact of total aortic arch repair in preventing late aortic reoperation in patients with acute TAAD.

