8.3. Statistical Analysis

Statistical analyses will be conducted using Stata v. 15.1 (StataCorp LLC, Texas, USA) and SPSS v. 29.0 (IBM Corporation, Armonk, NY, USA) statistical softwares. Continuous variables and outcomes will be summarized as mean and standard deviation as well as median and interquartile range. Categorical variables and outcomes will be reported as counts and percentages. A p<0.05 will be set for statistical significance. Differences between the study groups will be evaluated using the Fisher's exact test, the Chi-square test, the linear-by-linear association test, the Mann-Whitney test and the Kruskal-Wallis test. The McNemar test and paired samples T-test will be used in case of

analysis of paired groups. Propensity score matching will be performed to balance treatment strategies for baseline differences. A propensity score will be estimated using a non-parsimonious multilevel mixed-effects logistic regression considering the cluster effect of the participating centers whose results may be affected by the referral pathway, surgical techniques and perioperative care. Multilevel mixed-effects logistic regression model will include all available baseline variables. One-to-one propensity score matching will be performed using a caliper width of 0.2 of the standard deviation of the estimated logit. Standardized differences <0.10 will be considered an acceptable imbalance between the matched cohorts. The estimated propensity score will be also included into regression models to adjust for multiple confounders or for analysis within its strata.

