12.5. End of the study

The study will be concluded with the end of patient recruitment: 31-Dec-2025. This will represent also the end of follow-up and data collection.

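### The non-inferiority size of 100 per group in 8.2 names no time point and assumes complete follow-up; read at 8 years it gives about 81% power, not 90%

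*Protocol*

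**What the plan says.** Section 8.2 of the Protocol names total arch repair as a main research topic and gives two sample sizes: 163 per group for superiority, and a smaller one for non-inferiority.

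The non-inferiority calculation starts from a study that "reported a freedom from distal reoperation after ascending aortic resection at 8 years of 95.3" per cent. The plan then says "we assumed a freedom rate from distal aortic reoperation of 95" per cent, this time with no year attached, and concludes: "delta=0.1, power 0.90, one-sided confidence 97.5%), the required sample size would be 100 patients per each group". Nothing is added for incomplete follow-up, death or loss. The section ends by taking 5% of patients as total arch repairs and calling 4000 patients enough, which is 0.05 × 4000 = 200 total arch patients.

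The observation window is set elsewhere. Section 7.5: "Only TAAD patients undergoing open heart surgery between 1 January 2010 and 31 December 2024 will be retrospectively retrieved". Section 12.5 gives 31 December 2025 as the end of the study and adds: "This will represent also the end of follow-up and data collection".

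The reoperation outcome in the Synopsis and in 6.2 is a cumulative incidence up to the last follow-up control. Treatment groups are to be compared after matching (8.3, Statistical Analysis): "One-to-one propensity score matching will be performed".

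**The concern.** A binomial variance p(1−p)/n is right only if each patient's status at the chosen time is known. Here potential follow-up runs from 1 year (operated at the end of 2024) to 16 years (operated at the start of 2010). Anyone operated on in 2018-2024, 7 of the 15 operation years, cannot be observed for 8 years. An 8-year estimate from such data has a larger variance than the formula assumes, so the 90% printed beside 100 per group does not describe this design.

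At stake is how a reader uses the number. Someone planning the arch analysis could take 100 matched pairs as sufficient for 90% power, and could see the 200 expected total arch patients as a two-fold reserve that matching may freely use up.

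**Working it through.** **Inputs.** From 8.2: freedom 95% in both groups, margin 0.10, one-sided 0.025, power 0.90, and 8 years as the only horizon mentioned. From 7.5 and 12.5: entry over 15 years, cut-off at 16 years. From 5.1: 30-day mortality of 16.9-18% in cited registries. Assumed: uniform accrual, constant reoperation hazard, true equality of the groups and, where used, late mortality of 2-5% per year. The Protocol gives no late mortality.

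**1. The plan's own figure.** (1.960 + 1.282)² = 10.507, and n = 10.507 × 2 × 0.95 × 0.05 / 0.10² = 99.8, so 100. The printed number is correct for a fully observed proportion.

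**2. Dates alone.** Let λ = −ln(0.95)/8, and let C(t) be the fraction still under potential observation: C(t) = 1 for t < 1 and (16 − t)/15 afterwards, so C(8) = 8/15 = 53%. The Greenwood variance at 8 years, per patient, is

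V = 0.95² × ∫₀⁸ λ / Y(t) dt, with Y(t) = s₀ · exp(−(λ + μ)t) · C(t),

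where 1 − s₀ is early mortality and μ is late mortality, both treated as censoring. With no deaths (s₀ = 1, μ = 0), V = 0.0621 against the binomial 0.0475, an inflation of 1.31.

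- Standard error of the difference at 100 per group: √(2 × 0.0621/100) = 0.0352.
- Power: Φ(0.10/0.0352 − 1.96) = Φ(0.88) = 81%.
- Size for 90%: 99.8 × 1.307 = 130.5, so 131 per group.

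Simulated Kaplan-Meier power in this case was 82%.

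**3. Death as a competing event.** With an 8-year cumulative incidence of 5%, the simulated standard deviation of the Aalen-Johansen estimate at n = 100 was 0.0247-0.0251 across mortality settings from none to 18% early plus 5% per year. With 0.0250, power is Φ(0.10/(√2 × 0.0250) − 1.96) = Φ(0.87) = 81%; the range is 80-82%. Known deaths do not reduce power on this scale.

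**4. Deaths censored (Kaplan-Meier).**

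| Early deaths | Late mortality per year | Inflation | Power at 100 | N per group for 90% | Power at 200 |
|---|---|---|---|---|---|
| 0 | 0 | 1.31 | 81% | 131 | 98% |
| 17% | 0 | 1.58 | 73% | 157 | 95% |
| 17% | 2% (assumed) | 1.72 | 70% | 172 | 94% |
| 17% | 3% (assumed) | 1.81 | 68% | 180 | 93% |
| 17% | 5% (assumed) | 1.98 | 63% | 198 | 90% |

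**5. Sensitivity.** At a 5-year horizon the dates alone give 86%. If the accrual rate doubles steadily over the 15 years, the dates alone give 78% at 8 years. If the 95% is a death-censored (net) freedom while the analysis uses cumulative incidence, the expected incidence falls below 5% and power at 100 per group is about 87-93% once deaths are included.

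**6. Matching.** If 80% of 200 total arch patients find a match (assumed), 160 pairs remain. Power over the rows of the table is then 83-95%.

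**The case against.** The case against is substantial, and most of it limits the point without removing it.

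- *There is no arithmetic slip.* True: 99.8 rounds to the printed 100. The fault lies in the model behind the formula and in the missing time point.
- *100 per group is not the planned size.* Also true. Section 8.2 rests on 4000 patients, hence 200 total arch repairs, and its superiority figure of 163 per group (whose derivation is not examined here) already exceeds 131. Section 8.1 expects more than 5000 patients, and the Synopsis and 13.3 more than 10000. At 5% these are 250 and 500 total arch patients, and even with inflation 1.98 power would be 95% and 99.9% if all were matched. A reader might infer that the registry is underpowered for the arch comparison; the documents do not support that.
- *Power as low as 63% is overstated.* This stands as a limit. A reader might take 63% as the expected power. It requires deaths to be censored although the Synopsis and 6.2 define a cumulative incidence and 8.2 itself faults a cited pooled analysis for ignoring competing risks. It also requires late mortality of 5% per year, which the Protocol does not give.
- *The 8-year horizon is inferred.* It is, but it is the only horizon in the calculation. At 5 years the dates alone still bring power below 90%.
- *The stated power may not be lost at all.* That holds, nearly or fully, if 95% is net freedom and the analysis is by cumulative incidence. Section 8.2 does not say so.

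**Conclusion.** The point holds in limited form. The 100 per group is the size for a fully observed proportion at an unnamed time. At the 8 years of the cited rate, the registry's own dates reduce power at 100 per group from 90% to about 81%, and about 131 per group are needed. The result is about the same, 80-82%, for a 5% cumulative incidence with death competing, which is the scale closest to the stated outcome. Both rest on uniform accrual and a constant reoperation hazard. Values of 63-73% belong only to an analysis that censors deaths, and those of 70% and below also to an assumed late mortality.

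The conclusion that 4000 patients suffice is not overturned. What shrinks is the apparent two-fold reserve: 200 against about 131 for cumulative incidence, and at worst 200 against 198 if deaths are censored, in both cases before any loss to matching.

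**What to change.** In 8.2:

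1. State the time point of the non-inferiority comparison, and whether death is a competing event or is censored.
2. Replace 100 per group by about 130 for a cumulative incidence at 8 years (about 157-198 if deaths are censored, with the mortality assumptions written out). Alternatively keep 100 and restate its power as about 80%.
3. Express adequacy as the number of matched total arch pairs expected, not the 200 total arch patients before matching.

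The cost is one recalculation and a few sentences. No extra enrolment, data collection or change of design follows. The only drawback is a less favourable printed figure, which the planned registry can still meet.

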8.3. Statistical Analysis

Statistical analyses will be conducted using Stata v. 15.1 (StataCorp LLC, Texas, USA) and SPSS v. 29.0 (IBM Corporation, Armonk, NY, USA) statistical softwares. Continuous variables and outcomes will be summarized as mean and standard deviation as well as median and interquartile range. Categorical variables and outcomes will be reported as counts and percentages. A p<0.05 will be set for statistical significance. Differences between the study groups will be evaluated using the Fisher's exact test, the Chi-square test, the linear-by-linear association test, the Mann-Whitney test and the Kruskal-Wallis test. The McNemar test and paired samples T-test will be used in case of

analysis of paired groups. Propensity score matching will be performed to balance treatment strategies for baseline differences. A propensity score will be estimated using a non-parsimonious multilevel mixed-effects logistic regression considering the cluster effect of the participating centers whose results may be affected by the referral pathway, surgical techniques and perioperative care. Multilevel mixed-effects logistic regression model will include all available baseline variables. One-to-one propensity score matching will be performed using a caliper width of 0.2 of the standard deviation of the estimated logit. Standardized differences <0.10 will be considered an acceptable imbalance between the matched cohorts. The estimated propensity score will be also included into regression models to adjust for multiple confounders or for analysis within its strata.

Logistic and linear regression analyses will be employed to identify independent risk factors for early adverse events with and without a stepwise approach. For the purpose of developing a risk scoring method from this registry, the study cohort will be randomly divided into two datasets, i.e. the derivation data set (75.0% of patients) and the validation data set (25.0% of patients). Univariate analysis will be performed on all candidate covariates of the derivation dataset to identify predictors of in-hospital mortality. Multiple logistic regression analysis will be then performed using the derivation dataset. A stepwise procedure with a bootstrap approach will be used, and 100 samples will be extracted with a size of 70% of the derivation dataset. A stepwise procedure will be applied to each sample (probability to stay = 0.05; probability to entry = 0.1). Variables selected in at least 50% of the stepwise procedures will be included in the regression model. Additional covariates were selected using a forward selection comparing the Akaike information criterion for the models with and without each covariate. The model with the lowest Akaike information criterion will be selected for each forward step, until the inclusion of a new covariate determined an increase in the Akaike information criterion value. The model will be tested in the validation data set for calibration, using the Hosmer-Lemeshow test, and for discrimination using the receiver-operating characteristic curve analysis. A comparison of the predictive ability of the new score with the current risk scoring methods for prediction of in-hospital mortality will be performed in the overall dataset as well as in the validation dataset using the DeLong test. The improvement of discrimination of the new score will be estimated by calculating the net reclassification index and the integrated discrimination improvement.

Interinstitutional and between-surgeons differences in terms of early outcomes will be evaluated using logistic regression. The risk-adjusted rate of adverse binary events at each center will be estimated by dividing the observed number of adverse events by the expected number of adverse events, and by multiplying this ratio by the average event rate of the overall series. The expected numbers of adverse events will be calculated with logistic regression. The estimated risk-adjusted rates of adverse events will be summarized as odds ratios and their 95% confidence intervals in caterpillar plots with the x-axis ordered for increasing adjusted rates.

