5. BACKGROUND AND RATIONALE

5.1. Background

Acute Stanford type A aortic dissection (TAAD) is a life-threatening condition. Surgery is usually performed as a salvage procedure and is associated with increased postoperative early mortality and morbidity (1). Although early mortality has declined during the last years (2), the recent The Nordic Consortium for Acute Type A Aortic Dissection registry including 1189 patients operated from 2005 to 2015 in 8 centers showed that 30-day mortality after surgery for acute TAAD was 18% (3). The multicentre, prospective German Registry for Acute Aortic Dissection Type A including 2137 TAAD patients operated from 2006 and 2010 documented a 30-day mortality of 16.9% (4). A more recent analysis of the Society of Thoracic Surgeon database including 7353 patients operated from 2014 and 2017 for acute TAAD reported a 30-day mortality of 17% (5). Furthermore, surgery for TAAD is often complicated by major adverse events such as stroke (5) and acute kidney failure (6), which may have a significant impact on late survival. In this scenario of significant postoperative mortality and morbidity, surgeon faces the controversial issue of the extent of surgical repair for acute TAAD by avoiding a major surgical repair with its possible increased risk of early adverse event. At the same time, the surgeon would need to decide on whether to resect aortic segments which may expose the patient to the risk of late complications at the level of the aortic root (7) as well as of the aortic arch or distal to it (8). Understanding the balance between the patient's conditions which may not allow extensive procedure and those treatment strategies which may limit the risk of late adverse events in patients who remain alive long after the surgery is essential for an appropriate management of TAAD. We aim to create the present multicenter European registry of surgery for acute TAAD (ERTAAD) to evaluate the contemporary early outcomes and late durability of different surgical strategies for acute TAAD in a large study population within a long follow-up period.

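### Section 8.2 calls 4000 patients enough by counting operated total arch patients, with no allowance for early deaths or failed matches, and one-to-one matching then leaves about 95% of limited-repair patients out of the matched analysis

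*Protocol*

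**What the plan says.** Section 8.2 (Sample Size Calculation) treats total arch versus more limited repair as a main question of the registry and gives two sizes.

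- Superiority: a cited pooled analysis "estimated a pooled hazard ratio on 0.73 (95%CI 0.56-1.18) of freedom from any late aortic reoperation for total arch replacement", and on that basis "a sample size of 163 patients per study groups would be enough to reject the null hypothesis (alpha 0.05, power 0.80").
- Non-inferiority: "we assumed a freedom rate from distal aortic reoperation of 95" per cent, with "delta=0.1, power 0.90, one-sided confidence 97.5" per cent, so that "the required sample size would be 100 patients per each group".

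It then links these sizes to the registry: "We assume that about 5% of patients have undergone total arch repair in this collaborative registry". From this it concludes that 4000 patients suffice.

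Section 8.3 (Statistical Analysis) fixes the matching: "One-to-one propensity score matching will be performed using a caliper width of 0.2 of the standard deviation of the estimated logit". The standardized-difference limit of 0.10 applies to the matched cohorts, and McNemar and paired t-tests are named for paired groups. The same section also uses the propensity score as a regression covariate and for analysis in strata. It names none of these approaches as primary.

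Section 5.1 (Background) gives early mortality from three sources. One "documented a 30-day mortality of 16.9" per cent; the other two report 17% and 18%.

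**The concern.** The sufficiency claim counts patients who had the operation. The outcome it is made for is late aortic reoperation, and one of the planned comparisons is between matched pairs. A patient who dies early cannot contribute a late reoperation, and a total arch patient with no control inside the caliper leaves the matched comparison. Section 8.2 allows for neither loss. A third loss is possible: the propensity model takes in all available baseline variables, while the section on avoiding bias rules out replacing missing values.

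There is also a question of efficiency. Total arch repair is the scarce group and limits precision, while limited repairs are plentiful. Fixing the ratio at one-to-one leaves most of that plentiful group out of the matched analysis. At stake is whether the claim for 4000 patients can be relied on, and whether the matched comparison uses the data already collected.

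**Working it through.** **Inputs.** From section 8.2: hazard ratio 0.73; alpha 0.05 and power 0.80; 95% freedom from reoperation; margin 0.10; one-sided 0.025 and power 0.90; 5% total arch repair; 4000 patients. From section 5.1: 30-day mortality 16.9–18%, used below as 17–18%. From section 8.1: more than 5000 patients. From the synopsis and section 13.3: more than 10000. The documents give no match rate, so the required rate is calculated.

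**1. The plan's own figures.**

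Non-inferiority: n = (1.960 + 1.282)² × 2 × 0.95 × 0.05 / 0.10² = 99.8, so 100 per group. This agrees exactly.

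Superiority, taken as two-sided:
- Schoenfeld: 4 × (1.960 + 0.842)² / (ln 0.73)² = 317 events, or 159 per group.
- Freedman: (1.960 + 0.842)² × (1.73 / 0.27)² = 323 events, or 162 per group.

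The stated 163 therefore reproduces as events per group. It would be a number of patients only if every patient were reoperated.

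**2. What 163 patients would give.** Take 95% freedom in the limited-repair group. This is section 8.2's own figure, though stated there for distal reoperation. The event proportions are 0.05 and 1 − 0.95^0.73 = 0.0368, mean 0.0434.
- Patients needed per group: 3655 (Schoenfeld) to 3724 (Freedman).
- With 163 per group there are 326 × 0.0434 = 14.1 events. Power = Φ(0.3147 × √14.1 / 2 − 1.96) = Φ(−1.37), about 9%.
- With an assumed 80% freedom instead: 905–923 per group, and about 22% power at 163.

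**3. Attrition against the stated sizes.** Total arch patients: 0.05 × 4000 = 200, which is 37 above 163. Early deaths at 17–18% take 34–36, leaving 166–164.

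| Registry | Total arch | After 17–18% deaths | Match rate for 163 pairs | Match rate for 100 pairs |
|---|---|---|---|---|
| 4000 | 200 | 166–164 | 98–99% | 60–61% |
| 5000 | 250 | 207.5–205 | 79–80% | 48–49% |
| 10000 | 500 | 415–410 | 39–40% | 24% |

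At 4000 patients and an assumed 80% match rate, 166 × 0.8 = 133 pairs remain. Non-inferiority power is then Φ(0.10 / √(0.095 / 133) − 1.96) = 0.96.

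**4. Controls left out of the matched set.** Limited repairs: 4000 − 200 = 3800, or 19 per total arch patient. If all 200 match, 1 − 200/3800 = 94.7% are left out; with 163 pairs, 1 − 163/3800 = 95.7%. The 19-to-1 ratio follows from the 5% assumption and does not depend on registry size.

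**5. What more controls would add.** For a fixed number of matched total arch patients, information is proportional to 1 / (1/r + 1/k). Here k is the number of controls each, and r is the event rate in total arch patients relative to controls.
- r = 1: four controls give 2 / 1.25 = 1.60 times the one-to-one information; two give 2 / 1.5 = 1.33.
- r = 0.73: four give 2.370 / 1.620 = 1.46; two give 2.370 / 1.870 = 1.27.

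These are ceilings, because some patients will find fewer controls and set weights cost something.

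At 95% freedom, take 149 matched total arch patients (90% of 166, assumed) and power = Φ(0.3147 / √(1/d₁ + 1/d₀) − 1.96), with d₁ and d₀ the events in the total arch and limited-repair groups.
- One-to-one: d₁ = 5.5, d₀ = 7.45; power about 8%.
- Four controls each: d₁ = 5.5, d₀ = 29.8; power about 10%.

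**The case against.** Several objections have force.

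- **4000 is a threshold, not the expected size.** Section 8.1 expects more than 5000 patients, and the synopsis and section 13.3 more than 10000. A reader might infer that the registry will have too few total arch patients for 163 pairs. The documents do not support that: at the larger sizes the required match rates are moderate, and the actual rate is unknown. What stands is that the claim made for 4000 has almost no room.
- **The non-inferiority target is robust.** It holds down to about 60% matched, so the attrition point bears on the superiority size only.
- **Matching is not the only analysis.** A reader might infer that limited-repair patients are discarded from the study. They are not, because the regression and stratified analyses can keep them all. The loss is confined to the matched analysis.
- **Early deaths are not strictly removed.** The synopsis counts reoperation from the index stay onward, so early deaths are competing events in a risk set that starts at surgery. The 17–18% is also for all such surgery, not total arch repair. Subtracting them is a planning approximation, but a reasonable one for late events.
- **One-to-one caliper matching is conventional.** It trades precision for closeness and is not an error. The case against it here rests on the 19-to-1 imbalance in the protocol's own assumption.

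**Conclusion.** The concern holds in a limited form. Section 8.2 counts operated patients and states no allowance for early death or failed matching. At 4000 patients, early deaths alone use 34–36 of the 37 spare total arch patients, so 163 pairs require 98–99% matched. This rests on the 5% share, on 17–18% mortality applying to total arch patients, and on treating early deaths as lost to the late comparison.

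The 163 is itself an event count, so no power percentage should be quoted with 163 patients per group as 80%. A reader might infer that more controls per total arch patient would bring the superiority comparison back to 80% power. They would not: the gain in information is at most about 1.5–1.6 times (about 1.3 with two controls), and at 95% freedom from reoperation power stays near 10%. The case for a higher ratio is better precision from data already collected. The changes should be made, but correcting attrition and ratio alone would not make the superiority claim valid.

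**What to change.** **Section 8.2.** State the superiority requirement in expected reoperation events. Also state it in matched total arch patients after expected early deaths and unmatched patients, with the assumed rates written down. This is a planning quantity only: matching should use all operated patients and baseline data, never survivors selected afterwards. Withdraw or restate the claim that 4000 patients are enough for superiority. The non-inferiority figure can stay, with its tolerance for match loss stated.

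**Section 8.3.** For total arch versus limited repair, use variable-ratio matching with up to four limited-repair patients per total arch patient. Keep the caliper and the 0.10 balance limit, and weight the matched sets. Replace McNemar and paired t-tests for this comparison by methods suited to matched sets of varying size. Keep the one-to-one match as a sensitivity analysis.

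**Cost.** Changed wording in two sections and modest programming, with no further enrolment. Second to fourth matches will be somewhat less close, which the caliper bounds and the balance table will show.

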13. FUTURE DEVELOPMENT

13.1. Implications for the Treatment of TAAD Patients

Analysis of the data from this collaborative registry will allow analysis of contemporary results of a large number of TAAD patients with a lengthy follow-up period. We expect that the multicentre nature of this registry will allow reduction in the risk of bias related to institutional volume and surgical experience. In fact, all the participating centers have an annually rate of at least 25 procedures for acute TAAD and have an aortic surgery program which would facilitate an adequate follow-up and management of possible late aortic events after primary repair of TAAD. Therefore, we expect to gather data which will provide important insights into the assessment of the operative risk of patients with acute TAAD and conclusive results on the value of different surgical and perfusion strategies for this emergency condition.

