13.2 Limitations

The retrospective nature is the main limitation of this registry. However, our aim is to investigate the long-term outcome (>10 years) of these patients and this may not be feasible with a prospective registry. Second, the prognostic impact of different treatment strategies will be analyzed using several statistical methods to adjust for baseline differences. However, the lack of randomization does not prevent the effects of confounding variables. Third, perioperative care may significantly vary between institutions as well as individual surgeons and their effects should be considered in all analyses.

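### The in-hospital mortality score is validated only in a random quarter of patients from the centres that built it, which checks overfitting there but not calibration in another centre

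*Protocol*

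**What the plan says.** All of the score's development and testing is set out in protocol section 8.3 (Statistical Analysis).

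- **Split.** "the study cohort will be randomly divided into two datasets, i.e. the derivation data set (75.0% of patients", and the rest form "the validation data set (25.0% of patients". The unit is the patient. Neither centre nor calendar period enters the division.
- **Model.** "Multiple logistic regression analysis will be then performed using the derivation dataset". No centre term is mentioned.
- **Variable selection.** A stepwise bootstrap procedure in which "100 samples will be extracted with a size of 70% of the derivation dataset". Nothing says that centres are resampled as units.
- **Calibration.** "The model will be tested in the validation data set for calibration, using the Hosmer-Lemeshow test". Discrimination is assessed in the same set by ROC analysis.

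No held-out centres, external cohort or centre-by-centre calibration are named for the score.

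On centre differences, the same section fits the propensity score with centre as a cluster, giving referral, technique and perioperative care as reasons. Section 13.2 goes further: "perioperative care may significantly vary between institutions as well as individual surgeons and their effects should be considered in all analyses". Section 8.3 also plans a comparison of centres by risk-adjusted rates. The synopsis (Statistical Considerations) allows a Bayesian hierarchical approach if between-centre variability is significant. Neither of these is tied to the score or its validation.

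**The concern.** When patients are split at random, each centre sends about three quarters of its patients to derivation and one quarter to validation. A centre with higher or lower mortality than its case mix predicts does so in both sets, in the same proportion. The centre effects therefore match between the two sets by design, and overall calibration in the validation quarter will look good whether centres differ a lot or not at all.

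A user of the score wants to know whether the predicted risk is right at their own hospital, which will often not be one of the contributors. Section 13.1 expects the registry to "provide important insights into the assessment of the operative risk of patients with acute TAAD". If centres differ as the protocol expects, a satisfactory result in the random quarter could be read as support for use elsewhere that it does not give. This is not a detail left for an analysis plan, since the protocol itself fixes the split and its unit.

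**Working it through.** The protocol gives no sample size, precision or power for the validation, so there is no figure of its own to reproduce. The check asks whether the planned validation result responds to centre differences.

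**Inputs from the protocol**
- Split: 75% / 25% of patients (section 8.3).
- Size: more than 10000 patients (synopsis, section 13.3) in 32 centres (synopsis); or more than 5000 patients (section 8.1) in 20 centres (section 7.1).
- Mortality: 17% at 30 days in a cited surgical database (section 5.1), used as a guide. The simulated rate was about 15%.

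**Assumed, because not stated:** the between-centre variation. It is expressed either as an ICC on the latent logistic scale or as the standard deviation tau of a centre intercept, with tau² = ICC/(1 − ICC) × π²/3. For ICC 0.05, tau² = 0.0526 × 3.290 = 0.173, so tau = 0.42. For ICC 0.01, tau² = 0.0101 × 3.290 = 0.033, so tau = 0.18.

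**Size of the validation set.** 0.25 × 10000 = 2500 patients and 2500 × 0.17 = 425 deaths; or 0.25 × 5000 = 1250 patients and 1250 × 0.17 ≈ 213 deaths.

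**Simulation.** Outcomes were generated from a logistic model with prognostic covariates and a random centre intercept. A model without centre was fitted in a random 75%. The observed/expected ratio (O/E) was computed in the other 25%. The true O/E of the fitted score was then computed in a new centre drawn from the same distribution.

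Results with four covariates, 10000 patients and 32 centres (95% ranges):

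| ICC | O/E in the random 25% | True O/E in a new centre |
|---|---|---|
| 0 | about 0.9-1.1 | 0.95-1.05 |
| 0.01 | about 0.9-1.1 | 0.74-1.32 |
| 0.02 | about 0.9-1.1 | 0.61-1.47 |
| 0.05 | about 0.9-1.1 | 0.50-1.79 |

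At ICC 0.10 the random-split range is again about 0.9-1.1.

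A separate simulation (five covariates, 300 runs per setting) applied the planned Hosmer-Lemeshow test under two units of splitting, again with 10000 patients and 32 centres:

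| tau | Rejection, random 25% of patients | Rejection, 25% of whole centres held out | O/E in the held-out centres, pooled |
|---|---|---|---|
| 0 | 8% | 9% | 0.90-1.10 |
| 0.2 | 8% | 17% | 0.85-1.21 |
| 0.3 | 7% | 24% | 0.79-1.24 |
| 0.5 | 8% | 44% | 0.73-1.35 |

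With 5000 patients in 20 centres the random-split O/E stays at about 0.87-1.15 and rejection at 7-10% for every tau. Whole-centre rejection is 8%, 14%, 24% and 45%.

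So the planned check gives the same answer whatever the centre effect. A check by centre does not.

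**The case against.** The strongest points on the other side are these.

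- **A random split is a legitimate internal check, and the protocol claims no more.** This stands. Section 8.3 speaks of a score from this registry and does not call the validation external. The sentence in section 13.1 concerns the registry's data in general. A reader might infer that the validation result is worthless, or that the protocol asserts validity in new centres. The documents support neither.
- **The size depends on an unstated variance.** This stands. With no centre differences the random split is adequate. But sections 8.3 and 13.2 themselves expect differences.
- **A narrow interval that misses new centres would not be evidence about the splitting unit.** This stands. A confidence interval for the pooled O/E in the validation set covers only about one new centre in five at ICC 0.05, but it does so under either unit: 20% and 20% in one set of runs, 21% and 22% in another. An interval for an average is not a prediction interval. The protocol also plans no O/E interval for the score. No weight is placed on coverage here.
- **Centre-level O/E is already planned.** This stands in part. If the regression behind the centre comparison in section 8.3 used case mix only, its ratios would nearly equal leave-one-centre-out ratios. But it compares centres' outcomes and is not linked to the score. The Bayesian option in the synopsis is conditional and changes neither the split nor the calibration test.
- **The loss of events to the split is small.** This stands. At 17% mortality derivation keeps 3750 × 0.17 ≈ 638 to 7500 × 0.17 = 1275 deaths, and no harm from the loss was shown.

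**Conclusion.** The point holds in a limited form. The only validation named for the score is a patient-level random quarter. It tests overfitting within the contributing centres and cannot detect miscalibration in another centre, although the protocol expects centres to differ and asks that their effects be considered in all analyses.

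How much this matters rests on an assumed between-centre variance. At ICC 0 nothing is lost. At ICC 0.01 the score could already predict mortality wrongly in a new centre by about a quarter to a third (O/E 0.74-1.32), and at 0.05 by about half to more than three quarters (0.50-1.79), with the validation result unchanged. These ranges also assume that centres differ only in baseline risk and that a new centre resembles the participating ones.

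The score is not among the listed primary or secondary objectives, so this is a cheap and worthwhile improvement to one planned product. It does not threaten the registry's main analyses.

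**What to change.** In the risk-score paragraph of section 8.3 (Statistical Analysis), replace the random 75/25 split by internal-external cross-validation by centre:

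1. Leave out each centre in turn, or a small group of low-volume centres, and repeat the whole selection and fitting procedure on the rest.
2. In the left-out centre, estimate the c-statistic, the O/E ratio and the calibration slope.
3. Pool these by random-effects meta-analysis and report a prediction interval for a new centre as well as the pooled mean. In simulation the leave-one-centre-out prediction interval for O/E covered 92-96% of new centres in every setting.
4. Fit the final score on all patients.

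Holding out whole centres once, making up about a quarter of patients, is a weaker fallback. It would need an interval that allows for between-centre variation, since the usual interval for the pooled result does not.

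The cost is a change of wording and about 20-32 repeats of a procedure already planned. No new data or patients are needed. Reported performance will look less favourable and less precise.
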